6.8. Patient Characteristics

Patient characteristics will include a summary of the following:

- Patient demographics [including age, sex, screening height and weight, race, ethnicity, and screening body mass index (BMI)] will be reported.
- Baseline disease characteristics including ECOG status, initial pathological diagnosis, disease stage, histopathological diagnosis grade.

Other patient characteristics will be summarized as deemed appropriate.

6.9. Treatment Compliance

Treatment compliance will not be calculated since Olaratumab and Pembrolizumab are administered intravenously.

6.10. Concomitant Therapy

All medications will be coded to the generic preferred name according to the current World Health Organization (WHO) drug dictionary. All concomitant medications listings will include both the term reported in CRF and the WHO dictionary term and if concomitant medication use is due to an adverse event (AE), the associated AE will also be listed.

Prior anti-cancer systemic therapy, radiotherapy and surgery will be summarized. Summaries will include the reason, type of therapy, number of prior regimens and drug name. Prior therapies will also be listed, including the patients response to prior therapy.

Anti-cancer systemic therapy, radiotherapy or surgery that occurs post discontinuation of study treatment is captured separately from concomitant medication as the existence of such

therapies can lead to censoring of time to event endpoints. Patients that received post discontinuation therapies will be listed and summarized.

6.11. Efficacy Analyses

6.11.1. Efficacy Definitions

The following definitions for efficacy endpoints will be used:

Overall response rate (ORR) is the proportion of patients who achieved a complete response (CR) or partial response (PR) out of all patients treated. Tumor responses will be measured and recorded using the appropriate guidelines [RECIST 1.1 (Eisenhauer et al. 2009)].

Best response is determined as the best response recorded from start of study treatment until PD or recurrence.

Disease Control Rate (DCR) is the proportion of patients who achieved a best response of complete response (CR), partial response (PR) or stable disease (SD) out of all patients treated.

Immune-related objective response rate (irORR) is defined as the proportion of treated patients achieving a best overall response of PR or CR per irRECIST, particularly, the best overall response by irRECIST closely related to confirmed response by RECIST. Immune-related ORR further captures responses after unconfirmed PD and does not require confirmation. For example:

- If the best response by RECIST v.1.1 is CR, then the best response by irRECIST is CR.
- If the best response by RECIST v.1.1 is PR, SD, or PD, the best response by irRECIST is the best response over the initial assessment (prior to PD by RECIST v.1.1) and the confirmation stage.

Overall, the best response by irRECIST should be the same or better than the best response by RECIST v.1.1 criteria. In addition, patients who do not have any postbaseline tumor response assessments for any reason are considered non-evaluable and will be included in the denominator when calculating the response rate.

Immune-related disease control rate (irDCR) is defined as the proportion of treated patients achieving a best overall response of CR, PR or SD per irRECIST.

[figure not shown]
Duration of Response will be calculated for ORR and is defined only for responders (ie. CRs and PRs). It is measured from the date of first evidence of a confirmed response to the date of first progression of disease or the date of death due to any cause, whichever is earlier. For each patient who is not known to have died or to have had a progression of disease as of the data-inclusion cut-off date, duration of response will be censored at the date of last objective response assessment prior to the date of any subsequent systemic anticancer therapy.

Duration of Stable Disease will be calculated only for patients with best response of stable disease, CR or PR. It is measured from the date of start of treatment to the date of first progression of disease or the date of death due to any cause, whichever is earlier. For each patient who is not known to have died or to have had a progression of disease as of the data-inclusion cut-off date, duration of stable disease will be censored at the date of last objective response assessment prior to the date of any subsequent systemic anticancer therapy.

[figure not shown]
Duration of response by irRECIST is defined from the date of first documented irCR or irPR (responder) to the date of irPD or the date of death due to any cause, whichever is earlier.

Graphic Example:

Scenario 1: The initial PD is confirmed at the next scan (consecutive PD). The efficacy variables by irRECIST and RECIST are the same.

Scenario 2: The initial PD is not confirmed at the next scan (non-consecutive PD). The efficacy variables by irRECIST and RECIST v.1.1 are different.

In addition, the best response after initial PD may be listed. Other efficacy analysis based on irRECIST may be performed for exploratory analysis.

Change in tumor size will be assessed in each patient with measurable disease using radiographic imaging. Tumor size is the sum of the tumor measurements for target lesions at each tumor evaluation. Change in tumor size is defined as the percent change in tumor size from

the baseline evaluation to the minimum post-dose evaluation. Other definitions of CTS may be explored (including specific time points, and AUC formulations).

Progression-free survival (PFS) time is defined as the time from the date of start of study treatment to the first date of PD (symptomatic or objective) or death due to any cause, whichever occurs first. For patients who are not known to have died or progressed as of the data-inclusion cut-off date, PFS time will be censored at the date of the last objective progression-free disease assessment prior to the date of any subsequent systemic anticancer therapy.

Immune-related progression-free survival (irPFS) is defined as the date from the treatment started date to the time of PD assessed by irRECIST.

- If the initial PD is confirmed, then the date of immune-related (ir)PD is the initial PD date by RECIST v.1.1.
- If the initial PD is unconfirmed, then the date of irPD is the date of second PD.

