8.3. Efficacy Evaluations

A secondary objective of both the Phase 1a and 1b portions of the study is to assess the following efficacy endpoints:

- ORR
- DCR
- DOR
- PFS
- OS

ORR, DCR, DOR, and PFS will be assessed according to RECIST v1.1 (Eisenhauer et al. 2009).

PFS is defined as the time from the date of study enrollment until the date of the first observed radiographically documented PD or death due to any cause, whichever comes first. Overall survival, including 1- and 2-year survival rates, is determined from the date of first treatment until death due to any cause.

Patients may continue to be treated with the combination therapy until a confirmed progression is documented per irRECIST.

Following computerized axial tomography (CT) scan or magnetic resonance imaging (MRI) during the screening period, investigators will assess tumor response modified for confirmation of progression (irRECIST) every 6 weeks (\pm 5 working days) for up to 24 weeks. Confirmatory scans will be preferably obtained at the next routine scheduled imaging time point (that is, 6 weeks) and no earlier than 4 weeks later. After 24 weeks, tumor assessments will be conducted every 12 weeks. Additional radiologic assessments are permissible at the discretion of the investigator. The method of assessment used at baseline should be used consistently for a patient throughout the trial. Refer to [Attachment 1](#) for details regarding the timing of specific efficacy measures.

Immune-Related RECIST (irRECIST)

Immunotherapeutic agents such as pembrolizumab may produce antitumor effects by potentiating endogenous cancer-specific immune responses. The response patterns seen with such an approach may extend beyond the typical time course of responses seen with cytotoxic agents, and can manifest a clinical response after an initial increase in tumor burden or even the appearance of new lesions. Standard RECIST may not provide an accurate response assessment of immunotherapeutic agents such as pembrolizumab (Wolchok et al. 2009). Therefore, RECIST 1.1 will be adapted to account for the unique tumor response characteristics known to occur with pembrolizumab treatment (irRECIST) and additionally assessed using these criteria. Adaptations for irRECIST are detailed in [Attachment 8](#).

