Attachment 8. RECIST 1.1 and irRECIST

Response and progression will be evaluated in this study using the international criteria proposed by the New Response Evaluation Criteria in Solid Tumors (RECIST): Revised RECIST Guideline (version 1.1; Eisenhauer et al. 2009) and by the immune-related Response Evaluation Criteria in Solid Tumors (irRECIST).

RECIST 1.1

Measurability of Tumor at Baseline

Tumor lesions/lymph nodes will be categorized at baseline as measurable or nonmeasurable. Measurable disease is defined by the presence of at least 1 measurable lesion.

Measurable

Tumor lesions: Measured in at least 1 dimension (longest diameter in the plane of measurement is to be recorded) with a minimum size of:

- 10 mm by computed tomography (CT) or magnetic resonance imaging (MRI) scan (slice thickness \leq 5 mm)
- 10 mm caliper measurement by clinical exam (non-measurable lesions if cannot be accurately measured with calipers)
- 20 mm by chest X-ray.

Malignant lymph nodes: To be considered pathologically enlarged and measurable, a lymph node must be \geq 15 mm in short axis when assessed by CT scan (CT scan thickness recommended to be \leq 5 mm).

Nonmeasurable

All other lesions, including small lesions (longest diameter $<$ 10 mm or pathological lymph nodes with \geq 10 to $<$ 15 mm short axis) as well as truly nonmeasurable lesions. Lesions considered truly non-measurable include: leptomeningeal disease, ascites, pleural/pericardial effusions, lymphangitis cutis/pulmonis, inflammatory breast disease, lymphangitis involvement of skin or lung, abdominal masses/abdominal organomegaly identified by physical exam that is not measurable by reproducible imaging techniques.

Special Considerations for Lesion Measurability

Bone lesions:

- Bone scan, PET scan, or plain films are not considered adequate imaging techniques to measure bone lesions.

- Lytic bone lesions or mixed lytic-blastic lesions, with identifiable soft tissue components, that can be evaluated by cross sectional imaging techniques such as CT or MRI, can be considered measurable lesions if the soft tissue component meets the definition of measurability.
- Blastic bone lesions are non-measurable.

Cystic lesions:

- Simple cysts should not be considered as malignant lesions (neither measurable nor nonmeasurable)

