Complete Response (CR): Disappearance of all target lesions. Any pathological lymph nodes (whether target or non-target) must have reduction in short axis to <10 mm. Tumor marker results must have normalized.

Partial Response (PR): At least a 30% decrease in the sum of diameter of target lesions, taking as reference the baseline sum diameters.

Progressive Disease (PD): At least a 20% increase in the sum of the diameters of target lesions, taking as reference the smallest sum on study (including the baseline sum if that is the smallest). In addition to the relative increase of 20%, the sum must also demonstrate an absolute increase of at least 5 mm. The appearance of one or more new lesions is also considered progression.

For equivocal findings of progression (for example, very small and uncertain new lesions; cystic changes or necrosis in existing lesions), treatment may continue until the next scheduled assessment. If at the next scheduled assessment, progression is confirmed, the date of progression should be the earlier date when progression was suspected.

Stable Disease (SD): Neither sufficient shrinkage to qualify for PR nor sufficient increase to qualify for PD, taking as reference the smallest sum diameters while on study.

Not Evaluable: When an incomplete radiologic assessment of target lesions is performed or there is a change in the method of measurement from baseline that impacts the ability to make a reliable evaluation of response.

Evaluation of Nontarget Lesions

Complete Response: Disappearance of all nontarget lesions and normalization of tumor marker level. All lymph nodes must be non-pathological or normal in size (<10mm short axis).

Non-CR/ non-PD: Persistence of 1 or more nontarget lesions and/or maintenance of tumor marker level above the normal limits.

Progressive Disease: Unequivocal progression of existing nontarget lesions. The appearance of 1 or more new lesions is also considered progression.

Not Evaluable: When a change in method of measurement from baseline occurs and impacts the ability to make a reliable evaluation of response.

Evaluation of Best Overall Response

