4.1.2. Secondary Objectives

The secondary objectives of the Phase 1a portion of the study are:

- To characterize the pharmacokinetics (PK) and pharmacodynamics (PD) of olaratumab when administered in combination with pembrolizumab
- To determine the immunogenicity of olaratumab when administered in combination with pembrolizumab
- To document any antitumor activity of olaratumab when administered in combination with pembrolizumab as assessed by:
 - Objective response rate (ORR) using Response Evaluation Criteria in Solid Tumors (RECIST) v1.1 and immune-related RECIST (irRECIST)
 - Disease control rate (DCR) using RECIST v1.1 and irRECIST
 - Duration of response (DOR) using RECIST v1.1 and irRECIST
 - Progression-free survival (PFS) using RECIST v1.1 and irRECIST
 - Overall survival (OS)

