4.2.2. Secondary Objectives

The secondary objectives of the Phase 1b portion of the study are:

- To document any antitumor activity of olaratumab when administered in combination with pembrolizumab as assessed by:
 - ORR using RECIST v1.1 and irRECIST

- DCR using RECIST v1.1 and irRECIST
- DOR using RECIST v1.1 and irRECIST
- PFS using RECIST v1.1 and irRECIST
- OS
- To characterize the PK and PD of olaratumab when administered in combination with pembrolizumab
- To determine the immunogenicity of olaratumab when administered in combination with pembrolizumab

[figure not shown]
5. Study Design

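### The SAP counts symptomatic progression as a PFS event; the protocol counts only radiographic progression or death, so PFS as defined in the SAP is not the RECIST v1.1 PFS that both documents name

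*SAP*

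**What the plan says.** SAP 6.11.1 gives this definition of PFS: "time from the date of start of study treatment to the first date of PD (symptomatic or objective) or death due to any cause". Patients not known to have progressed or died are censored at their last objective progression-free assessment before any new systemic anticancer therapy.

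The protocol differs. Section 8.3 states: "PFS is defined as the time from the date of study enrollment until the date of the first observed radiographically documented PD or death". The same section says that "ORR, DCR, DOR, and PFS will be assessed according to RECIST v1.1".

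The SAP's own objectives carry the RECIST label: "Progression-free survival (PFS) using RECIST v1.1 and irRECIST" in 4.1.2 for Phase 1a and "PFS using RECIST v1.1 and irRECIST" in 4.2.2 for Phase 1b. Protocol 5.2.1.2 and 5.2.2.2 list the same objectives.

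Attachment 8 of the protocol sets out RECIST 1.1. For target lesions, progression is "At least a 20% increase in the sum of the diameters of target lesions" from the smallest sum on study, with an absolute rise of at least 5 mm. Unequivocal nontarget progression and new lesions also count.

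SAP 6.11.2 commits to Kaplan-Meier curves, medians if the data are mature, and rates at, for example, 3, 6 and 12 months.

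**The concern.** The SAP rule admits an event type that neither the protocol definition nor RECIST 1.1 recognises. A patient judged to have progressed on symptoms, with no objective progression, is an event on that date under the SAP. Under the protocol the same patient has a later event or is censored. A PFS curve built from the SAP rule could be reported as RECIST v1.1 PFS when it is not.

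The comparison with irPFS is also affected. SAP 6.11.1 ties irPFS to the RECIST v1.1 progression date when the first progression is confirmed, and says of that case: "The efficacy variables by irRECIST and RECIST are the same". If symptoms came before the confirmed scan, PFS would end at the symptomatic date and irPFS at the scan date. Part of any gap between the two could then come from the symptomatic rule rather than from unconfirmed progression.

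The visible text of the SAP neither defines symptomatic progression nor says how to date it, so two programmers could derive different PFS times from the same data.

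**Working it through.** **Comparing the text**

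| Item | SAP 6.11.1 | Protocol 8.3 and Attachment 8 |
|---|---|---|
| Progression event | Symptomatic or objective | Radiographically documented; RECIST v1.1 |
| Symptoms as a criterion | Yes | No |
| Death | Event | Event |
| Start | Start of treatment | Study enrollment |
| Label in objectives | RECIST v1.1 and irRECIST | RECIST v1.1 and irRECIST |

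The difference in start date matters little: protocol section 4 defines an enrolled patient as one who has received a dose.

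Amendment history does not explain the difference in events. The SAP was approved on 15 February 2017, after Amendment (a) of 7 February 2017. The amendment rationales in protocol 5.1 and the Amendment (c) summary mention no change to the PFS definition.

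SAP 6.3 allows sensitivity analyses with other censoring rules but commits to none. SAP 6.1 lets derivations follow updated sponsor standards. Neither says which PFS definition is the main one.

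**Illustrative size**

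The documents give no PFS figure to reproduce. They state neither an expected median PFS nor the share f of first progressions seen only as symptoms. The following are assumptions: f = 10% or 20%, and a SAP-rule median of 3 months with constant hazard. The scan schedule (6-weekly to 24 weeks, then 12-weekly) is from protocol 8.3.

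SAP rule: S(t) = 0.5^(t/3), so S(6) = 0.5^2 = 0.250.

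Protocol rule, by what happens after the symptoms:

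- **(a) Objective progression or death follows after a delay d.** S(6) = (1 − f) × 0.25 + f × 0.5^((6 − d)/3).
  - d = 30 days (0.99 months): 0.256 (f = 0.1) and 0.263 (f = 0.2).
  - d = 6 weeks (1.38 months): 0.259 and 0.269.
  - Shift +0.6 to +1.9 points; medians 3.1 to 3.3 months.
  - If objective progression is instead found at the next scheduled scan (simulated), S(6) is 0.253 and 0.256, a shift of +0.3 to +0.6 points.
- **(b) No later event is recorded and the patient is censored.**
  - At the last scan (Kaplan-Meier on 1,000,000 simulated patients): about 28% and 32%, shift about +3 to +7 points, medians 3.3 and 3.6 months.
  - At the symptomatic date: 0.25^(1 − f) = 0.287 and 0.330, shift +3.7 and +8.0 points.
- **(c) The event is counted only at death, with exponential residual survival.** S(6) = (1 − f) × 0.25 + f × R(6), where R(6) is the probability of being alive at 6 months for a patient whose symptomatic date follows the SAP curve.
  - Residual median 3 months: R(6) = 0.25 × (1 + 2 ln 2) = 0.597, giving 0.285 and 0.319.
  - Residual median 6 months: R(6) = 2 × 0.5 − 0.25 = 0.75, giving 0.300 and 0.350.
  - Shift +3.5 to +10.0 points.

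A separate simulation detected objective progression only at scheduled scans and censored symptomatic patients at their last scan. With f = 20%, 6-month PFS was 21% (SAP rule) against 28% (protocol rule) for an assumed true median of 2.5 months, and 38% against 46% for 4 months.

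**Scale against sampling error**

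Protocol 10.1.1 plans 31 patients at the recommended dose. With f = 10% to 20%, about 3 to 6 of them would be affected (31 × 0.1 = 3.1; 31 × 0.2 = 6.2). An observed 8/31 (26%) has an exact 95% CI of 12% to 45%.

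**The case against.** Counting symptomatic progression is a defensible choice. It can only add events or bring them forward, so it cannot flatter the treatment. The radiographic rule censors patients who deteriorate and change therapy, which can be informative; case (b) shows PFS rising under it. This stands, and it is the reason to keep the symptomatic rule as a sensitivity analysis. It does not make the SAP rule RECIST v1.1 PFS.

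The numerical effect may be very small. If patients are still scanned on schedule, the 6-month shift is below 1 point. The study schedule lists imaging at the safety follow-up visits, and patients who stop for reasons other than progression have 6-weekly progression follow-up. However, a patient recorded as having progressed on symptoms may fall outside that follow-up, which also ends at new anticancer therapy. The larger shifts in (b) and (c) rest on assumed inputs, and none of the figures is a bound.

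The statement about confirmed progression belongs to a graphic example built on scans and may simply not contemplate an earlier symptomatic date. That is fair: it is supporting evidence, not the core of the point. In addition, the irPFS definition in SAP 6.11.1 mentions no death event, so PFS and irPFS differ for another reason that the change proposed here would not remove.

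Finally, with about 37 patients and patient-level listings of lesion data, response and PFS (SAP 6.11.2), a symptomatic-only event should be traceable. That would help a careful reader of the report but does not settle the definition.

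**Conclusion.** The point holds. The mismatch in definition is certain: the SAP event set differs from the protocol's and from the RECIST v1.1 label used in both documents, and no other text resolves it. Whether the reported figures move is conditional on at least one patient having symptomatic progression dated before, or without, objective progression.

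Under the assumptions above, the protocol rule gives a 6-month PFS from less than 1 point to about 10 points above the SAP rule's 25.0%. That is smaller than the sampling error with about 31 patients. PFS is secondary and descriptive in both phases and SAP 6.5 plans no hypothesis testing, so no test or decision rule changes. This should be corrected before database lock, but it does not threaten the study's primary safety objective.

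**What to change.** In SAP 6.11.1:

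1. Define the PFS event as objective progression by RECIST v1.1 as set out in Attachment 8, or death from any cause, measured from first dose. Objective progression includes caliper-measured lesions where Attachment 8 allows them ("10 mm caliper measurement by clinical exam"). Align the terms for radiographic documentation and study enrollment in protocol 8.3 with this.
2. Keep the present censoring rule, and state that it also applies to patients who stop for symptomatic deterioration without an objective event.
3. Add one labelled sensitivity analysis that also counts symptomatic progression, dated at the recorded date of treatment discontinuation for that reason. That is the date of the decision to stop, not of symptom onset, but it is already collected. This analysis shows how far informative censoring could matter.

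The cost is SAP wording, derivation code, one extra analysis, and a wording change in protocol 8.3 at the next amendment. Protocol 6.3 already collects the date of and reason for discontinuation. The visible text does not show whether the recorded reason separates symptomatic from objective progression; check this before programming the sensitivity analysis.

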7.5. Concomitant Therapy

No other chemotherapy, radiotherapy, immunotherapy, cancer-related hormone therapy, or experimental drugs will be permitted while the patients are on this study. The need for any form of radiotherapy will be cause for early discontinuation from study treatment (palliative radiotherapy is permitted if clinically indicated, after discussion with the Lilly CRP/CRS). In addition, any disease progression requiring other forms of specific antitumor therapy will also necessitate discontinuation from study treatment. Appropriate documentation for all forms of premedications, supportive care, and concomitant medications must be captured on the eCRF. Replacement hormonal therapy initiated before study entry will be allowed.

Patients should receive full supportive care with the exception that the routine use of G-CSF is not permitted during this study. Patients should not receive G-CSF prophylactically in any cycle. G-CSFs may only be used for patients who have ANC<0.5 × 10⁹, neutropenic fever, or documented infections while neutropenic. G-CSFs must be discontinued at least 24 hours before the start of the next cycle of treatment. Should the use of hematopoietic colony-stimulating factors (CSFs) be necessary, follow the American Society of Clinical Oncology (ASCO) recommendations for the use of CSFs (Smith et al. 2006). If clinically indicated at any time during the study, erythropoietin and packed red blood cell transfusions may be used according to ASCO guidelines (Rizzo et al. 2008).

All concomitant medications should be recorded throughout the patient's participation in the study.

7.5.1. *Supportive Care Guidelines for Olaratumab*

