- ^b **30-day and 90-day Safety follow-up** begins the day after the patient and the investigator agree that the patient will no longer continue study treatment and lasts approximately 90 days (± 7 days). The date of this agreement is to be reported on the CRF as the date of discontinuation from study treatment. Visit 801 should occur approximately 30 days (± 7 days) after the decision to discontinue treatment. Visit 802 begins 1 day after the 30-day safety follow-up period ends and lasts approximately 60 days. If it is deemed to be in the best interest of the patient to start a new anti-cancer treatment prior to the scheduled end of the follow-up visits, the visit duration may be shortened. In this case, the follow-up assessments should be completed prior to the initiation of the new therapy.
- ^c **Long-term follow-up (Visits 803-8XX)** begins the day after 90-day safety follow-up is completed.
Follow-up for progression: Patients that discontinue study treatment for reasons other than progression will be followed every 6 weeks (± 7 days) until PD or initiation of other anticancer therapy. Additional radiologic assessments are permissible at the discretion of the investigator.
Follow-up for survival: All patients will be followed every 2 months (± 7 days) for the first 2 years, then every 6 months (± 14 days) until the patient's death or overall study completion.
- ^d A window of ± 3 days will be permitted due to holidays, weekends, inclement weather or other unforeseen circumstances, including unexpected changes in patient schedules, and will not count as a protocol deviation. In later cycles, longer delays may be allowed in consultation with Lilly medical representative.

I5B-MC-JGDQ(b) Continued Access Period

	Continued Access Period ^a		Comments
	Visit 501 - 5XX	Follow-Up Visit 901 ^b	
	21-day cycle		
Relative Day within a Cycle^c	1	8	
Olaratumab	X	X	
Dosing information	X		
PK sampling / Immunogenicity			
CTCAE v4.0 grading	X	X	

CCI

Abbreviations: AE = adverse event; CTCAE = Common Terminology Criteria for Adverse Events; eCRF = electronic case report form; IRR = infusion-related reaction; PK = pharmacokinetics; SAE = serious adverse event.

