The best overall response is the best response recorded from the start of the study treatment until the earliest of objective progression or start of new anticancer therapy, taking into account any requirement for confirmation. The patient's best overall response assignment will depend on the findings of both target and nontarget disease and will also take into consideration the appearance of new lesions. The Best Overall Response will be calculated via an algorithm using the assessment responses provided by the investigator over the course of the trial.

Time Point Response

It is assumed that at each protocol-specified time point, a response assessment occurs. (When no imaging/measurement is done at all at a particular time point, the patient is not evaluable (NE) at that time point.) Table ATT.8.1 provides a summary of the overall response status calculation at each time point for patients who have *measurable disease* at baseline.

Table ATT.8.1. Time Point Response: Patients with Target (\pm Nontarget) Disease

Target Lesions	Non-Target Lesions	New Lesions	Overall Response
CR	CR	No	CR
CR	Non-CR/non-PD	No	PR
CR	Not evaluated	No	PR
PR	Non-PD or not all evaluated	No	PR
SD	Non-PD or not all evaluated	No	SD
Not all evaluated	Non-PD	No	NE
PD	Any	Yes or No	PD
Any	PD	Yes or No	PD
Any	Any	Yes	PD

Abbreviations: CR = complete response; NE = not evaluable; PD = progressive disease; PR = partial response; SD = stable disease.

Table ATT.8.2 is to be used when patients have *nonmeasurable* disease only.

Table ATT.8.2. Time Point Response: Patients with Nontarget Disease Only

Nontarget Lesions	New Lesions	Overall Response
CR	No	CR
Non-CR/non-PD	No	Non-CR/non-PD ^a
Not all evaluated	No	NE
Unequivocal PD	Yes or No	PD
Any	Yes	PD

Abbreviations: CR = complete response; NE = not evaluable; PD = progressive disease.

^a non-CR/non-PD is preferred over SD for nontarget disease.

Frequency of Tumor Re-Evaluation

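### PFS, DOR and duration of stable disease are censored at new systemic therapy only when no later event is recorded, so whether a switcher is censored depends on a later death

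*SAP*

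**What the plan says.** SAP 6.11.1 runs PFS from the start of study treatment "to the first date of PD (symptomatic or objective) or death due to any cause, whichever occurs first". No event is excluded because new therapy came first. The censoring sentence is conditional: "For patients who are not known to have died or progressed as of the data-inclusion cut-off date, PFS time will be censored". For those patients only, follow-up is cut back to the "date of the last objective progression-free disease assessment prior to the date of any subsequent systemic anticancer therapy".

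DOR has the same structure. The event runs "to the date of first progression of disease or the date of death due to any cause, whichever is earlier", and the cut at new systemic therapy is again limited to patients with no known death or progression at data cut-off. Duration of stable disease follows suit, and Protocol Attachment 8 puts the same condition on DOR censoring.

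In Protocol Attachment 1, the long-term follow-up footnote continues progression follow-up "until PD or initiation of other anticancer therapy". The same footnote keeps all patients in survival follow-up until death or study completion.

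No other section settles the matter. SAP 6.10 says that post-discontinuation "therapies can lead to censoring of time to event endpoints" but gives no rule. SAP 6.3 allows optional sensitivity analyses under other, unnamed censoring rules, and its sentence on withdrawals does not mention new therapy. Protocol 8.3 and 10.8 have no new-therapy rule for PFS.

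**The concern.** A censoring rule should use only what is known at the censoring time. Here, whether a patient leaves the risk set at the switch is decided by whether a death is recorded months afterwards. That is informative censoring.

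Two coherent strategies exist. Treatment policy ignores the switch for everyone, so later events count and event-free switchers stay at risk. Censor-at-switch removes every switcher at the switch. The written rule applies the first to patients who die and the second to patients who live, so its curve cannot be read as either.

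PFS and DOR are secondary objectives in both phases. Protocol 10.9 plans a 12-month landmark for PFS if the data are immature, and by then late post-switch deaths have entered the curve. With about 31 patients at the recommended dose, a few switchers can visibly move it.

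**Working it through.** No sample size, event count or precision figure in the plan depends on this rule, so there is no stated result to reproduce. The check applies the rule literally.

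**1. Two patients.** Both switch at month 2 without PD, with the last scan at month 1.4. One dies at month 13 and is an event at 13 months. The other is event-free at a month-14 cut-off and is censored at 1.4 months. Up to the switch their histories are identical.

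**2. Ten illustrative patients, Kaplan-Meier.** Six do not switch and have PD at months 1.4, 2.8, 4.2, 5.6, 8.4 and 11.2. Four switch at month 2 (last scan 1.4); two of them die at months 9 and 13, and two are event-free at month 14.

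- Written rule: one event among 10, then two censored, leaving 7. 6 months: 9/10 × 6/7 × 5/6 × 4/5 = 0.51. 12 months: that × 3/4 × 2/3 × 1/2 = 0.13.
- Censor every switcher: one event among 10, then four censored, leaving 5. 6 months: 9/10 × 4/5 × 3/4 × 2/3 = 0.36. 12 months: 0.
- All events count: 4 of 10 have an event by month 6, giving 0.60, and 7 of 10 by month 12, giving 0.30.

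**3. Position against treatment policy.** The written rule and the all-events rule share the same events and dates. They differ only in that the written rule removes event-free switchers early. Each Kaplan-Meier factor is 1 − d/n. With the same d and an n that is never larger, the written curve can never lie above the all-events curve.

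**4. Position against consistent censoring.** A patient who switches and later dies stays in the risk set, with no progression observable, until the death. This lifts the early curve, and the death then lowers the later curve. Which effect dominates depends on the inputs.

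The documents give none of these inputs, so all are assumed. PFS is exponential. Between 10% and 30% of patients are assigned a switch at 1 to 4 months, and it takes effect only if PD has not come first. Median survival after the switch is 12 months and the cut-off falls at 12 to 24 months. Scans are every 6 weeks to week 24 and then every 12 weeks, as in Protocol 8.3. There are 400,000 simulated patients per row. Each cell shows written / censor all / all events.

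| Median PFS (months) | Switch before PD | 6-month PFS | 12-month PFS |
|---|---|---|---|
| 3 | 6% | .258 / .247 / .272 | .068 / .062 / .089 |
| 3 | 11% | .265 / .242 / .294 | .074 / .060 / .116 |
| 3 | 17% | .271 / .236 / .313 | .079 / .059 / .142 |
| 5 | 14% | .439 / .427 / .465 | .189 / .186 / .234 |
| 9 | 8% | .625 / .627 / .635 | .386 / .395 / .405 |
| 9 | 17% | .619 / .621 / .639 | .374 / .393 / .413 |

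At a 3-month median, written minus censor-all at 6 months is .258 − .247 = 1.1 points, rising to .271 − .236 = 3.5 points. At a 9-month median the 12-month difference is .386 − .395 = −0.9 and .374 − .393 = −1.9 points. A harsher case (9-month median, 25% switching, median post-switch survival 6 months) gives .334 against .389, or −5.5 points.

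**5. Scale.** With N = 31 and true 6-month PFS of 0.25, the sampling SD is √(0.25 × 0.75 / 31) = 0.078. The gap in most rows is well inside that noise.

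**The case against.** The strongest reply is that the rule hardly matters. The study tests no hypothesis, the endpoints are secondary, and the gaps above are smaller than the sampling error. That stands, and it limits the priority. It does not make the rule right, because the reported curve still has no clear meaning.

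The affected group may also be small. The SAP counts symptomatic PD as an event. Visits 801 and 802 include radiological assessment, and Attachment 1 asks for follow-up assessments before new therapy starts. Both favour finding PD before a switch. This stands, and it is why the low end of the switching range is shown. PFS, DOR and post-discontinuation therapies are also listed by patient, so each case can be traced.

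Consistent censoring is not perfect either. In the 3-month scenarios with 11% and 17% switching it gives about .24 at 6 months against a true .25. That shortfall comes from back-dating censoring to the last scan while the simulation dates PD exactly; censoring at the switch itself returns about .25. Any censor-at-switch analysis also assumes that switchers would otherwise have fared like non-switchers. These are ordinary limits of a defined quantity.

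A reader might extend the point further than the documents support:

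- **Radiotherapy and surgery.** The cut names only systemic therapy, while SAP 6.10 also covers radiotherapy and surgery. But 6.10 concerns treatment after discontinuation and says only that censoring can follow. Protocol 7.5, where "palliative radiotherapy is permitted if clinically indicated", concerns patients on study. Whether such treatment should censor PFS is a design preference.
- **Best response.** Attachment 8 ends it at new therapy ("until the earliest of objective progression or start of new anticancer therapy") and the SAP does not. With scheduled scans stopping at the switch, few later scans could change it.
- **irPFS and irDOR.** The SAP states no new-therapy censoring rule for either, so this asymmetry is not shown there.

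**Conclusion.** The point holds for PFS, DOR and duration of stable disease. Followed exactly, the written rule makes a switcher's censoring depend on a later death, and no other section corrects it.

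The size is modest and rests wholly on assumed switching rates, PFS medians and post-switch survival. Against consistent censoring, 6-month PFS is about 1 to 3.5 points higher at a 3-month median with 6% to 17% switching. At a 9-month median with 8% to 17% switching and 12-month post-switch survival, 12-month PFS is about 1 to 2 points lower; shorter post-switch survival and more switching widen this. The written curve never exceeds the all-events curve.

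A reader might infer that the rule always lengthens PFS and DOR. The 9-month rows show that it need not. A reader might also infer a larger effect on DOR because responders will be few. That was not computed, and the documents give neither the number of responders nor their switching rate. A post-switch death is a PFS or DOR event under the SAP's definitions and should not be described as a progression.

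This should be changed, but nothing primary or confirmatory depends on it.

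**What to change.** In SAP 6.11.1, apply one rule to every patient who starts new therapy without prior progression. For PFS, DOR and duration of stable disease, censor at the last adequate assessment before the first new systemic anticancer therapy, whatever is recorded later. This option fits the data collected, because scheduled progression scans end at the switch. Align the DOR sentence in Protocol Attachment 8 at the next amendment.

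Name the all-events (treatment-policy) version as a sensitivity analysis, with event-free switchers kept at risk instead of censored before the switch. State beside it that, after a switch, it captures almost only deaths, so progression in that interval is unobserved. Report how many patients switched without progression and how many of them later died.

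The cost is SAP wording and one extra table, with no new data collection. The downside is slightly fewer events, because post-switch deaths become censored observations in the main analysis.
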